Transdermal alcohol monitors can provide noninvasive, continuous monitoring of alcohol use by detecting ethanol diffused through the skin.^{27,31} Secure Continuous Remote Alcohol Monitor (SCRAM) anklet (Alcohol Monitoring Systems, Inc.) is the most widely used transdermal monitor but is designed to be used for law enforcement purposes.³² However, wider application of SCRAM anklet in clinical and intervention settings is limited by its shortcomings including its large size, high cost, and social stigma.^{20,25,29} The newest generation of wrist-worn alcohol monitor (BACtrack Skyn) is designed for consumer use and

addresses these limitations. The device looks like a fitness tracker, is inexpensive, samples up to every second, and transmits and shows data in real-time via a smartphone app. These advantages make this wrist-worn alcohol monitor a potentially ideal tool to be incorporated into smartphone-based intervention for alcohol use. However, prior to its application in research, thorough validation investigations of the monitor are needed. In this project, we will validate the Skyn monitor among 20 HIV+ drinkers and 20 HIV- drinkers (as comparison group) in both laboratory and field settings.

Fig.1. BACtrack Skyn Alcohol Monitor

5. Specific Aims:

Aim 1: Assess the validity and reliability of the Skyn monitor through comparison with laboratory grade breathalyzer in two fixed-dose lab alcohol administration sessions (Sec. 4.3, 4.5)

Hypothesis 1a: The monitor will be able to detect alcohol use at a low threshold (e.g., one drink).

Hypothesis 1b: The parameters of transdermal alcohol concentration (TAC) (e.g., peak, time-to-peak, area under the curve) will be correlated with number of drinks and breath alcohol concentration (BrAC).

Hypothesis 1c: The TAC readings in two lab sessions will show high correlation (test-retest reliability).

Aim 2: Validate Skyn monitor in daily life using a 2-week ecological momentary assessment (EMA), and evaluate its acceptability and usability for daily alcohol monitoring (Sec.4.4)

Hypothesis 2a: The monitor detected drinking episodes will correspond with self-reports in EMA.

Hypothesis 2b: The TAC readings will correlate with number of drinks in each drinking episode.

Exploratory Aim: Explore factors (e.g., gender, HIV status) that may be associated with individual differences in monitor readings (e.g., peak, time-to-peak, correlation with consumption level).

6. Research Plan:

Overview

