We will encourage each HIV+ drinker to refer up to 3 other drinkers, including persons that they suspect are HIV-, to participate. This will provide a comparison sample of HIV- drinkers who are likely to be of similar age and socio-economic status as the HIV+ participants. Additional inclusion criteria include self-reported ≥5 days with at least 1 alcoholic drink, and ≥1 days with at least 3 drinks (the level of alcohol consumption in lab sessions) in the past 30 days. Exclusion criteria include recent addiction treatment or treatment seeking; urine positive for illegal drugs except THC (not applicable to those who are only invited to do field test); past & current alcohol withdrawal; severe alcohol use disorder (DSM-5); meeting criteria for current nicotine dependence (not applicable to field only participants) or current substance use disorder (excluding mild cannabis use disorder and mild/moderate alcohol use disorder); medical conditions (other than HIV) contraindicating alcohol; pregnancy/breastfeeding in women; psychosis or other severe psychiatric conditions. Current use of antidepressant medication will not be an exclusion criteria for participants who are only completing the field test portion of the study.

Screening

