EMA: Participants will be instructed to enter information on each drinking session using an EMA app called mEMA (ilumivu, Inc.). This app is developed for mobile-based ecological momentary assessment to collect real-time data in daily life (Fig. 4). Researchers can create questions and set up the prompt type for each question (e.g., scheduled, or on-demand). In this study, participants will be asked to initiate an on-demand survey in the app whenever they start a drinking episode. This survey include questions regarding the drinking episode such as the starting and ending times of each drink, types of drinks, drinking amount, and food intake. To capture any potentially missed self-initiated entry at the time of drinking, the EMA app will also prompt questions at a fixed schedule every morning to ask about alcohol consumption in the past 24 hours. The morning prompts will also include reminders to check the battery life of the monitor and to upload EMA data, and report issues they had with the Skyn monitor. The app uses cloud storage and researchers can access data in real time once uploaded by the participants. We will contact participants via phone call if we notice any issues (e.g., missing daily prompt, reported monitor malfunction) so that these issues can be resolved in time. Participants will receive \$70 (\$5/day) and a bonus of \$70 if they complete ≥80% of the EMA questions, wear the monitor ≥80% of the time, and return it to the lab.⁵²

Lab Session 2. For those who are asked to complete all study components, after completing the two-week field test, participants will return to the lab for a second drinking session. The procedures will be the same as in Lab Session 1 with only one exception: Instead of training/practice with the monitor and app, participants will be asked to complete a survey on the acceptability and usability of Skyn and its app. The survey will include questions adapted from established instruments such as the System Usability Scale⁵³ and the Mobile App Rating Scale⁵⁴, with some open-ended questions about user-desired features. Before dismissal, the RA will help uninstall the apps on the participant's phone. Payment structure is the same as in Lab Session 1.

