Analysis plan for Aim 2. *Validate Skyn monitor in daily life using a 2-week ecological momentary assessment (EMA), and evaluate its acceptability and usability for daily use.* H2a. Agreement between monitor and self-reports in EMA. Using the same definition of a successful detection and procedure of determining drinking episode in monitor data as in

H1a, we will calculate the detection rates by self-reported number of drinks. A receiver operating characteristic (ROC) curve will be plotted. H2b: Relationship between TAC and number of drinks. First, simple correlations will be calculated to examine the association between TAC (peak, AUC) and self-reported number of drinks using all drinking episodes. Second, a multilevel analysis will be used to examine the association between TAC (peak, and AUC) and number of drinks accounting for nested data within person. Acceptability and Usability. Ratings of the Skyn monitor will be summarized on aspects such as wearability, ease to operate, satisfaction with the product, and willingness to wear.

Analysis plan for Exploratory Aim. *Explore factors that may be associated with individual differences in monitor readings.* T-tests or Chi-square will be used to examine group differences (e.g., male vs. female, HIV+ vs. HIV-) in TAC parameters (i.e., peak, time-to-peak) and their relationships with # of drinks and BrAC.

Sample size and power. This is for how many participants need to complete the study. For Aim 1, the sample size was based on prior laboratory validation studies of transdermal alcohol monitors.^{36,45,57} Also, power analysis shows that a sample size of 40 will give us 80% power to detect a correlation $\geq .60$. For Aim 2, power analysis shows that $n = 40$ will give us 90% power ($\alpha = .05$) to detect an effect size $\geq .13$ in a multilevel analysis with $r = .60$ between measures.^{58,59} For Exploratory Aim, $n = 20$ in each group can give us 80% power to detect a large difference ($d \geq .80$).

7. Possible Discomforts and Risks:

Potential risks in this study include:

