1. *Breach of confidentiality:* Our study will collect data on alcohol use from persons living with HIV. HIV infection is a very sensitive health condition. Breach of confidentiality could occur via communications with participants, loss of research data, and transfer of data. Consequently, procedures have been established to ensure the protection of this information, described in the Adequacy of Protection against Risks section.
2. *Alcohol consumption:* Potential risks in this study were identified in accordance with the recommended guidelines on ethyl alcohol administration in human experimentation put forth by the National Advisory Council on Alcohol Abuse and Alcoholism (2005). Steps taken to minimize these risks were also developed in accordance with these documents.

A number of medical conditions could potentially be worsened by acute alcohol administration (e.g., liver disease, cardiac abnormality, pancreatitis, diabetes, neurological problems, and gastrointestinal disorders). As a result, participants with such medical problems or who currently take medications contraindicating alcohol consumption at the level in this study will be excluded.

Alcohol self-administration in a research study by individuals who are severely alcohol dependent as evidenced by current withdrawal, a history of withdrawal or diagnosis of current severe alcohol use disorder may pose a risk to their health and safety. Alcohol self-administration in a research study by individuals who are seeking treatment for alcohol dependence or who have recently engaged in intensive treatment for alcohol dependence may compromise their efforts to reach or to maintain abstinence or moderate levels of alcohol use.

Alcohol may cause nausea in high doses, however, nausea is not expected at the doses that will be consumed in this sample of frequent heavy drinkers. Only current drinkers who had at least 1 drinking day with 3 or more drinks in the past month are selected for the study, thus ensuring that any amount of alcohol consumed during an alcohol administration session is less than or equal to an amount of alcohol they consume on their own.

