Recruitment: The HIV+ drinkers will be recruited from the existing Florida Cohort registry (a database of PLWH who are consented to be contacted for research) managed by the Southern HIV and Alcohol Research Consortium and from the Consent2Share registry. We will focus on recruiting participants living in North Florida (n = 237, 60% male, 70% drank alcohol in past year) within 50 miles of the data collection site. The racial distribution of these participants is 40% white, 53% black, 3% Latino, and 4% other (primarily mixed race). We expect to get a similar distribution in our sample. We expect similar racial distribution of the HIV- drinkers, and some additional HIV-positive drinkers, as we will use participant referrals to recruit HIV- drinkers. They are likely to come from similar demographic background.

Screening: Potential participants will be contacted via phone call using their contact information in the registry or call our research staff if referred by other participants. A trained research assistant (RA) will introduce the study and ask a few screening questions (e.g., past 30 day use of alcohol) if the participant expresses interest. If the participant meets preliminary eligibility, the RA will schedule an in-person screen. At the outset of the in-person screening appointment, picture identification (i.e., passport, driver's license or state-issued identification card) is examined in order to verify the participant's identity and to ensure that they are 21 years or older. This ensures that no alcohol consumption on the part of individuals under age 21 will take place in this study. The in-person screen will include breath alcohol test, drug and pregnancy test (women), HIV test if HIV status unknown, timeline follow back (TLFB) for past 30-day alcohol use, medical history, and diagnostic interview for substance use disorder/withdrawal. The screen will take approximately 2 hours, and participants will receive \$20 for completing the screen. Participants who come to their in-person screen as originally scheduled will be provided an additional \$10 payment. For participants who are HIV+, we will ask them to bring in medical records of their most recent HIV lab values (CD4/Viral load) at any in-person appointment and will provide \$20 compensation for doing so.

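### Is the Aim 2 claim of 90% power for an effect of .13 unsupported because the number of measures per person is not given?

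*Combined protocol and SAP*

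**What the plan says.** The Aim 2 power statement is in section 6, under Sample size and power: "For Aim 2, power analysis shows that $n = 40$ will give us 90% power", at alpha .05, to detect an "effect size $\geq .13$ in a multilevel analysis with $r = .60$ between measures". The 40 are completers. The sentence cites references 58 and 59; the reference list in the available copy stops at 32.

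Hypothesis 2b in section 5 reads: "The TAC readings will correlate with number of drinks in each drinking episode". The analysis plan for H2b has two steps. The first is a simple correlation of TAC (peak and AUC) with "self-reported number of drinks using all drinking episodes". The second is a multilevel model of the same association that allows for nesting within person; the sentence describing it does not name its unit.

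Four other places bear on how many records a person can supply:

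- The field test lasts two weeks (Field Test).
- The app will "prompt questions at a fixed schedule every morning to ask about alcohol consumption in the past 24 hours" (EMA).
- Eligibility requires "self-reported ≥5 days with at least 1 alcoholic drink" in the past 30 (Participants).
- The risk section speaks of nausea not being expected "in this sample of frequent heavy drinkers" (section 7, Alcohol consumption).

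No expected number of episodes per person is given, although screening includes a "timeline follow back (TLFB) for past 30-day alcohol use" (Protection against Risks, Screening).

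**The concern.** Power in a repeated-measures or multilevel design depends on the number of measures per person as well as on the number of people. A correlation between measures cannot be turned into a power figure without that count, nor an effect of .13 without its metric. Both are absent.

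The most natural reconstruction of the 90% implies 13 or 14 measures each. An abstinent day yields no drinking episode, and the eligibility rule guarantees only a few drinking days per fortnight. If the calculation assumed 14 records and the model received 3, the stated power for a weak association would be well above the true one. A reader could then take a null or imprecise H2b result as evidence against an association of .13 when the study had little chance of seeing it.

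**Working it through.** **Inputs.** From the power sentence: n = 40, alpha = .05, effect .13, ρ = .60. From the field test: 14 days. From eligibility: at least 5 drinking days in 30. The metric and the number of measures m are not given, so m is varied below.

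**1. Reproducing the stated 90%.** Take .13 as Cohen's f for a within-person repeated-measures F test (assumption):

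λ = f² · n · m / (1 − ρ), df1 = m − 1, df2 = (n − 1)(m − 1).

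At m = 14: λ = .0169 × 40 × 14 / .40 = 23.66, df 13 and 507, power 91.1%.

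| m | 2 | 3 | 5 | 7 | 10 | 12 | 13 | 14 | 15 |
|---|---|---|---|---|---|---|---|---|---|
| Power | 43% | 49% | 62% | 72% | 82.5% | 87.5% | 89.4% | 91.1% | 92.5% |

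The plan's figure corresponds to one record per field day, which is what the morning prompt produces. Other readings behave differently. With .13 as a correlation, 90% is reached at about 15 to 17 measures. With .13 as f² or η², power exceeds 99% at every m. With .13 as d, power is only 43% at m = 30.

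**2. The test H2b plans.** The table above is for an omnibus test of differences among occasions. H2b asks for the association of TAC with number of drinks, which is a slope with one degree of freedom. Keep the same λ with df1 = 1 and df2 = nm − n − 1. Power is 82% at m = 5, 89% at 6, 93% at 7 and 98% at 10; 90% is reached at m = 6.3.

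**3. A more explicit slope model.** Take a random-intercept model with standardised slope .13, residual variance 1 (.60 between persons, .40 within), and a share q of drink-count variance lying between persons. The values of q, and the reading of .60 as a residual intraclass correlation, are assumptions.

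Information = n · [(m − 1)(1 − q)/.4 + (mq + 1 − q)/(.4 + .6m)], λ = .13² × information.

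For m = 10 and q = .3: 40 × [9 × .7/.4 + 3.7/6.4] = 40 × (15.75 + .578) = 653.1. Then λ = .0169 × 653.1 = 11.04 and power is 91%.

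| Episodes per person | q = 0 | q = .3 | q = .6 |
|---|---|---|---|
| 3 | 47% | 39% | 29% |
| 5 | 75% | 62% | 45% |
| 7 | 89% | 78% | 58% |
| 10 | 97% | 91% | 74% |
| 14 | >99% | 98% | 87% |
| m for 90% | 7.2 | 9.6 | 15.6 |

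**4. The worst case for data yield.** At the eligibility minimum, with one episode per drinking day, 5/30 × 14 = 2.33 episodes per person, or 40 × 2.33 = 93 in all. Using Fisher's z, power = Φ(atanh(r) · √(N − 3) − 1.96):

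- r = .40, N = 93: Φ(.4236 × 9.487 − 1.96) = 98%.
- r = .40 with design effect 1 + 1.33 × .60 = 1.8, so N = 93/1.8 = 51.7: Φ(.4236 × 6.98 − 1.96) = 84%.
- r = .60: above 99% either way.

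**The case for a change.** The strongest case for acting is that the 90% is stated without conditions, while under every model with a plausible reading of .13 it depends on a count the plan never gives. Hypothesis 2b is about episodes, a day-level model that includes abstinent days answers a somewhat different question, and at 3 to 5 episodes per person power for .13 is 29% to 75% in the random-intercept model. Writing the count down would be cheap.

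The omission stands, and so does the conclusion that 90% power for .13 at episode level cannot be confirmed from the documents. The step from there to a defective plan does not. The 13 to 14 threshold belongs to an omnibus test that H2b does not use, so fewer episodes than that need not mean less than 90%. The 2.3 episodes is a floor for entry, and the protocol itself expects frequent heavy drinkers. The multilevel model's unit is unnamed, so a daily model using the morning reports is open to the analysts. The metric and method may be set out in the two cited references, which this copy does not list. A replacement power table would need a between-person variance share and a residual correlation that the documents do not supply, so it would exchange one unverified figure for several.

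**Conclusion.** No change to the plan follows. The power sentence leaves out the number of measures, the unit and the effect-size metric, but it contains no demonstrated error: under the Cohen's f reading it gives 89% to 91% at 13 to 14 measures, matching daily records over two weeks. For the slope that H2b will estimate, 90% power for .13 needs roughly 6 to 16 measures per person, and three of the four slope models tried need fewer than 10.

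What remains uncertain is confined to weak associations. A monitor validation turns on whether TAC tracks drinks strongly, and correlations of .40 to .60 keep at least 84% power even at the eligibility floor. H2b has no decision rule tied to the 90%. The number of analysable episodes will be known when the model is fitted, and the confidence interval for the slope will show what was and was not detectable. This rests on the assumed metric, on reading .60 as an equal correlation among measures, and on the assumed range for between-person variation in drinks.
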